**Part 3; Text/telephonic follow-up for safety (Day 2-7)**

On day 2-7 the parent/legal guardian (or patient if aged 16 to <18) will be contacted via text message (if possible), asking if the patient has experienced any side effects following discharge from the ED. If the reply is “yes” or the person does not respond to the text, the site investigator will attempt to contact them by phone to obtain further information about these adverse events. A total of 3 attempts will be made to make telephone contact. If all attempts are unsuccessful, the patient’s General Practitioner (GP) may be contacted for any relevant follow-up information. For further guidance on assessments, see Study Assessment Chart in Table 1.

Table 1: Study Assessment Chart

Visit Number and Name	1 Screening	2 Baseline and IMP Treatment	3 Follow-up (phone)
Study day	1	1	2-7
Study Activities			
Signed Informed Consent	X		
Allocation of participant ID	X		
Inclusion/Exclusion Criteria	X		
Type of injury*	X		
Demographics*	X		
Relevant Medical and surgical history*	X		
Recent and Concomitant medication* g)	X	X	X
Weight*	X		
Peripheral oxygen saturation*		X	
Pulse rate*		X	
Respiratory rate*		X	
Sedation score a)		X	
Pain intensity assessment* b)	X	X	
Administration of IMP c)		X	
Adverse events/ Serious adverse events d)		X	X
Nasal tolerability e)		X	
Feasibility and Treatment satisfaction questions f)		X	

\* if data from assessments performed prior to ICF signature are part of normal ED procedure they can be used in the study.

- a) Sedation will be assessed immediately after pain intensity assessments using the UMMS score at baseline and at 10, 15, 20, 30, 45 and 60 min post-IMP. If a second dose of IMP is needed the sedation score will be performed at the same time points relative to the second dose.
- b) Pain assessment will be performed using age-appropriate scales and they will be performed at screening, at baseline (before IMP administration), and at 10, 15, 20, 30, 45, 60 min post IMP. If a second dose of IMP is needed, the pain assessment timepoints will continue for 60 min after last IMP or until additional analgesics or procedures needs to be initiated. Unscheduled pain assessments should be done during any potentially painful intervention (e.g. during the application of a plaster cast for a fracture), prior to rescue medication or prior to premature study withdrawal.
- c) IMP will be administered to the participant while sitting in an upright position using the appropriate strength depending on the participant's weight. See more info in the IMP section and in the IMP manual.
- d) Adverse events will be collected spontaneously at all visits using open questioning.
- e) Nasal tolerability and irritation will be assessed using combined participant reported symptoms and investigator examination/inspection of the nasal cavities. Nasal tolerability will be performed twice; appr 30 min and 60 min after the *last* IMP administration (following pain, sedation and vital signs assessments).
- f) Treatment satisfaction will be addressed by asking the standardized questions "*How satisfied are you with the study drug that you/your child received? Please think about how it helped their pain, how it was given, any side effects, and how quickly you/your child recovered*". Respondents will answer using a 5-point Likert scale (very unsatisfied, unsatisfied, neutral, satisfied, very satisfied). Feasibility (i.e. acceptance of nasal administration) will be addressed by the healthcare staff asking the child: *If you were in this situation again*

and needed pain medication, would you like to receive the nasal spray? If not possible by the child, the parent/legal guardian will assess nasal acceptability.

g) Any medication given for AEs during the time from enrolment to follow up should be entered in the eCRF. Any 'rescue medication' (described as additional analgesics due to insufficient effect of IMP during the 60 min after the last dose of IMP), should be entered in the eCRF. The time given should also be noted.

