#### 4.3.12 Text/telephonic follow-up for safety

On day 2-7 the parent/legal guardian (or patient if aged 16 to <18 if in accordance with local legislation) will be contacted via text message, asking if the patient has experienced any side effects following discharge from the ED. If the reply is "yes" or the person does not respond to the text, the site investigator will attempt to contact them by phone to obtain further information about these adverse events. A total of 3 attempts will be made to make telephone contact. If all attempts are unsuccessful, the patient's General Practitioner (GP) may be contacted for any relevant follow-up information. The patient/ legal guardian(s) may, at any time during the study, contact the Principal Investigator, to discuss any drug experiences if needed. If it is not possible to reach the parent/legal guardian or the GP for the follow up phone call (on Day 2-7), then it should be stated that the patient is lost to follow up.

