### 6.3.2 Definitions of Adverse Events

#### **Adverse Event (AE):**

An AE is any untoward medical occurrence in a clinical study participant administered a pharmaceutical product and which does not necessarily have a causal relationship with this treatment. An AE can therefore be any unfavourable and unintended sign (including clinically significant abnormal values from relevant tests, such as clinical safety laboratory tests, ECGs, vital signs), symptom, or disease temporally associated with the use of an IMP, regardless of whether it is considered related to the IMP.

A baseline symptom is any medical event in a clinical study subject that occurs after he/she signed the ICF up until the first administration of IMP.

A treatment emergent AE (TEAE) is any AE not present, prior to the initiation of IMP administration or any event already present that worsens in either intensity or frequency following exposure to the IMP.

Only TEAEs are collected in this study (i.e., events occurring between screening and the first IMP administration are regarded as baseline symptoms and should not be recorded in the AE log in the eCRF).

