##### **Adverse Events**

The number of subjects with adverse events, with possible treatment related adverse events, and with serious adverse events (SAE) will be summarised using counts and percentages of subjects by age groups. The number and percentage of subjects with adverse events by body system and preferred term will be summarised by age group. Adverse event severity and relationship to treatment will be summarised by body system, preferred term, and age group. Separate tables may be produced for SAEs depending on the number of SAEs occurring in the study. A 95% confidence interval will be computed for each percentage/proportion of adverse events.

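### The Day 2-7 follow-up screens for 'side effects', although the primary endpoint counts AEs of any cause and Table 1 requires open questioning, so AEs may be missed among families who reply 'no'

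*Combined protocol and SAP*

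**What the plan says.** The Protocol Outline makes the number and percentage of participants with AEs an endpoint of the first primary objective. Section 6.3.2 counts an event as an AE "regardless of whether it is considered related to the IMP".

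For the period after discharge, section 4.2 (Part 3) and section 4.3.12 give the same procedure. On Day 2-7 the parent or guardian (or the patient from age 16) is sent a text "asking if the patient has experienced any side effects following discharge from the ED"; section 4.2 adds that this is done where possible. After a 'yes' or no reply, "the site investigator will attempt to contact them by phone to obtain further information about these adverse events". Up to three calls are tried, and then the GP may be asked. If neither the family nor the GP can be reached, "then it should be stated that the patient is lost to follow up". Neither section describes a step after a 'no'. Section 4.3.12 also allows families to contact the Principal Investigator at any time.

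Table 1 labels the same visit as a phone follow-up and marks AEs/SAEs and concomitant medication for it. Section 4.1 also describes Part 3 as a phone call. Footnote d states: "Adverse events will be collected spontaneously at all visits using open questioning". Footnote g states: "Any medication given for AEs during the time from enrolment to follow up should be entered in the eCRF".

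On analysis, the FAS is everyone dosed and serves the primary and secondary objectives (section 7.2). For AEs, section 7.4.1 says: "A 95% confidence interval will be computed for each percentage/proportion of adverse events". The Protocol Outline rules out imputing missing safety data, and section 7.3 says that the amount of missing data will be reported.

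**The concern.** In ordinary use a side effect is something the drug caused. A family asked about side effects must therefore decide on cause before answering, whereas the endpoint is defined without regard to cause and relationship is a later grading step, tabulated in section 7.4.1.

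Scheduled assessment in the ED runs for 60 minutes after the last dose, or less if other analgesia or procedures begin (section 4.2). After discharge, Visit 3 is the only scheduled contact. Section 1.7.1 lists vomiting and dizziness among the most common AEs of the completed paediatric study. Section 1.3 lists nightmares and abnormal behaviour with anaesthetic doses of ketamine, and reports no such association at sub-anaesthetic doses. A parent could put events of this kind down to the injury or to another medicine and reply 'no' in good faith.

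Any event lost this way lowers the numerator of a primary endpoint. The loss would also be selective: events that families judge unrelated drop out, which could distort the table of AEs by relationship. The planned 95% interval reflects sampling error only and would not show either effect.

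**Working it through.** **Setting the passages side by side**

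- *What is counted:* AEs of any cause (section 6.3.2; endpoint in the Protocol Outline).
- *What is asked at Visit 3:* a yes/no question on side effects (sections 4.2 and 4.3.12, same term in both, so not a single slip).
- *How AEs should be elicited:* open questioning at all visits (Table 1 footnote d), with the AE row marked for Visit 3.
- *Mode:* phone in Table 1 and section 4.1; text first in sections 4.2 and 4.3.12.
- *A cause-neutral prompt already exists:* section 6.3 has the investigator ask about feeling unwell or unlike usual, but for the clinic visit.

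**Tracing each reply**

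- 'Yes': phone call.
- No reply: up to 3 phone attempts, then possibly the GP.
- 'No': no step described. Only unscheduled routes remain, such as the family contacting the Principal Investigator.

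The possible loss is therefore confined to families who reply 'no'.

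**The plan's own figures**

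The documents give no post-discharge AE rate and no capture rate. The only calculated figure is the efficacy sample size, which reproduces. With p0 = 0.60, p1 = 0.716, one-sided 5% and 80% power, the normal approximation gives 104.4. The continuity correction, 104.4/4 × (1 + √(1 + 2/(104.4 × 0.116)))², gives 112.9, so 113. Then 113/0.75 = 150.7, against the stated 150. This point does not depend on it.

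**Illustration only (every input below is assumed, apart from n = 150)**

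Let q be the proportion of children with a post-discharge AE and s the share of those children whose event is captured. Expected number missed = 150 × q × (1 − s):

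| q (children) | s = 75% | s = 50% | s = 25% |
|---|---|---|---|
| 5% (7.5) | 1.88 | 3.75 | 5.63 |
| 10% (15) | 3.75 | 7.50 | 11.25 |
| 20% (30) | 7.50 | 15.00 | 22.50 |

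These are losses in the post-discharge count. The primary endpoint moves less, because a child with an AE in the ED is already counted. If a proportion e has an AE in the ED, independently of later events, the any-AE proportion falls by (1 − e) × q × (1 − s). With q = 10% and s = 50%:

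- e = 0: 1 × 0.10 × 0.50 = 5 percentage points
- e = 20%: 0.80 × 0.10 × 0.50 = 4 points
- e = 50%: 0.50 × 0.10 × 0.50 = 2.5 points

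On the interval: 15 of 150 has an exact 95% CI of 5.7% to 16.0%. At 25% capture about 4 of 150 would be recorded (3.75 rounded), with CI 0.7% to 6.7%, which excludes the assumed true 10%.

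For a post-discharge event with true incidence 1%, the chance of recording at least one case is 1 − (1 − 0.01s)^150: 78% at full capture, then 68%, 53% and 31% at s = 75%, 50% and 25%. With no event recorded, the one-sided 95% upper bound, (1 − 0.05^(1/150))/s, rises from 2.0% to 2.6%, 4.0% and 7.9%.

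**The case against.** The strongest reply has three parts.

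*The message text is not in the protocol.* The reference to side effects is reported speech. Where the sponsor fixes a question, as for satisfaction and nasal acceptance, it is printed in full, and section 4.2 goes on to call the same events adverse events. The actual text might be neutral. This limits what can be said about effect. It does not remove the mismatch, because a site following the protocol finds only this term, twice.

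*There are other routes.* A reader might infer that the text is the only contact after discharge, or that a 'no' closes follow-up. The documents do not support either. Non-repliers and 'yes' repliers are phoned, the GP may be asked, and families may contact the Principal Investigator. That nothing follows a 'no' is inferred from silence, and section 4.2 points to Table 1, so the text could be read as a trigger within a visit that still has open questioning. What stands is that calls are tied to a 'yes' or no reply, and that a family seeing no link to the drug has little reason to make contact unprompted.

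*Missing follow-up may be handled later.* A reader might infer a rule that unreached children count as AE-free. No such rule is written: safety data are not imputed, missingness is reported, and detail is deferred to a separate SAP. Still, with the FAS as denominator and no other denominator given in section 7.4.1, an unreached child adds to the denominator and cannot contribute a post-discharge AE.

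**Conclusion.** The mismatch holds and should be corrected. Following the written procedure, post-discharge AEs that a family does not attribute to the drug may be missed among those who reply 'no'. For the events concerned, the effect on the count can only be downward. Events in the ED, which are collected by direct questioning and observation, are not affected.

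The size cannot be computed from the documents. The illustrative figures rest on assumed values of q, s and e and on independence between ED and later events; they show scale, not an estimate. A statement that AEs *are* undercounted would go too far.

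Two further inferences should be avoided. The medication gap is not a separate defect: for the period after treatment, footnote g names only medication for AEs and rescue medication, so it follows from the AE gap. Nor do sections 6.3.2 and 6.3.2.2 say who judges causality; only the SAE notification in section 6.3.4 asks the investigator for a preliminary view. The point therefore rests on the definition being cause-neutral, not on an assigned assessor.

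**What to change.** - **Sections 4.2 and 4.3.12:** replace the side-effects wording with a cause-neutral prompt in line with section 6.3, for example whether the child has been unwell or not their usual self in any respect, or has been given any medicine, since leaving the ED. Phone on any 'yes' or non-reply.
- **Table 1 and section 4.1:** reconcile the phone label with the text-first procedure, and state how footnote d's open questioning is met at Visit 3, including after a 'no'.
- **Section 7.4.1 or the separate SAP:** keep the overall AE proportion in the FAS. In addition, report AEs with onset after ED discharge separately, with children for whom follow-up was obtained as the denominator, and state the number lost to follow-up and the day of contact.
- **Do not restrict onsets to the end of Day 2** to even out the contact window. A child contacted during Day 2 does not cover that whole day, and the restriction would drop Day 3-7 onsets from the proportion. Reporting the day of contact is enough.

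The cost is a reworded message, a few more call-backs, one extra table and possibly a slightly higher reported AE proportion. The analysis part can go into the SAP, which is due before database lock.

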## 4.2 Clinic visits

### Part 1; Screening (Day 1)

Potentially-eligible participants and their parents or legal guardian will be provided with written information about the study. Families who state an interest in participation will be asked to provide written informed consent +/- assent, as appropriate for the age group in accordance with local legislation. A patient ID number will then be assigned.

Following completion of the informed consent form (ICF), a formal screening assessment will be conducted, including assessment of eligibility according to the study inclusion and exclusion criteria. Pain scoring within the screening assessment will be conducted using the following pain intensity scores:

Age  $\geq$ 9 years: A 0-10 numerical rating scale (NRS) scale (10).  
Age  $\geq$ 5 to  $<$ 9 years: The Wong-Bake FACES scale (14).  
Age  $\geq$ 1 to  $<$ 5 years: The FLACC scale (15).

The same pain scale will be used for all subsequent study pain scores for that patient.

Any preceding data from the routine ED triage assessment (such as demographics, injury type, pain score, concomitant medications, and vital signs) can be utilized and transferred onto the screening electronic Case Report Form (eCRF).

The screening assessment will also include documentation of participant demographics, past medical history, and concomitant medications. If not already undertaken at the routine triage assessment, the participant will be weighed. Where a participant's injury makes weighing impractical, an estimated weight will be documented.

Females participants that have reached menarche, will be asked if it is any possibility that they could be pregnant. If they respond yes, they will not be eligible for the study. Females participants that have reached menarche and who are sexually active will be asked to follow contraceptive guidance for 7 days following IMP administration.

For further guidance on assessments at screening, see Study Assessment Chart [Table 1](#).

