### Part 2; Baseline and IMP treatment (Day 1)

The baseline assessment will include a repeat pain score, sedation score, and measurement of the participant's vital signs (respiratory rate, pulse rate, oxygen saturation) if not already undertaken at

the routine triage assessment. Once the pre-treatment assessments are performed the IMP will be administered.

After administration of IMP, pain scores will be assessed at the following approximate intervals (10, 15, 20, 30, 45, 60 min post IMP), as specified in the Study Assessment Chart (Table 1). The actual timepoints for pain assessment relative to IMP administration will be recorded in the eCRF.

Unscheduled pain intensity scores will be measured and documented during any potentially painful intervention (e.g. during the application of a plaster cast for a fracture), prior to rescue medication or prior to premature study withdrawal.

Where pain relief at 10-15 min after the first IMP administration is insufficient (for example, a pain score >4/10 on NRS, or at the discretion of the treating investigator), a second IMP dose of similar strength and dose can be administered to the participant. In the case of insufficient pain relief after two doses of IMP, additional analgesic medication may be administered at the discretion of the treating investigator, in accordance with standard local practice. The medication, dose and time of administration will be recorded in the eCRF.

After administration of IMP, level of sedation, vital signs (pulse rate, peripheral oxygen saturation, respiratory rate), nasal tolerability and spontaneously reported adverse events will be assessed.

Pain scores and safety assessments should continue for 60 min after the last dose of IMP, or until additional analgesic treatment or procedures need to be initiated. For further guidance on assessments at the treatment and post-treatment visit (Part 2), see Study Assessment Chart, Table 1.

Feasibility and treatment satisfaction in relation to the IMP and route of administration will be assessed prior to ED discharge.

Treatment satisfaction will be addressed by using the following standardized question: *“How satisfied are you with the study drug that you/your child received? Please think about how it helped their pain, how it was given, any side effects, and how quickly you/your child recovered”*. Respondents will answer using a 5-point Likert scale (very unsatisfied, unsatisfied, neutral, satisfied, very satisfied).

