### 4.3.2 Pain intensity assessments

The pain resulting from injury causing the emergency visit will be quantified. The participant will be introduced to the age-appropriate pain scale and overall pain will be assessed, with no distinction made between spontaneous pain and any procedural pain.

Immediately prior to administration of the IMP (baseline), the pain intensity will be rated using the applicable tool (see below). Subsequent pain assessments will be performed at 10, 15, 20, 30, 45, and 60 min post IMP administration. If a second dose of IMP is administered after 10-15 min, the pain assessment schedule will be reset, and pain will be measured at 10, 15, 20, 30, 45, and 60 min after the second dose of IMP, or until additional analgesics or procedures needs to be initiated.

Unscheduled pain intensity scores will be measured and recorded during any potentially painful intervention (e.g. during the application of a plaster cast for a fracture), prior to rescue medication or prior to premature study withdrawal.

Age-appropriate pain intensity assessment tools will be used:

**Age ≥9 years:** The Numerical Rating Scale (NRS) will be used. The NRS scales consists of a Likert scale, anchored with numbers 0-10, with 0 marked "No pain" and the right end (10) marked "Worst pain imaginable". The patient will state the number representing their current level of pain, and the study staff will circle the applicable number on the CRF page (see [Appendix A](#)).

**Age ≥5 to <9 years:** The visual analogue scale modified with six faces developed by Wong-Baker (Wong-Baker FACES pain rating scale) will be used. Numerical values (0, 2, 4, 6, 8, 10) are listed for each face (Wong et al, 2001, see [Appendix B](#)).

**Age 1 to <5 years:** The study investigator will provide an assessment of pain, using the FLACC scale (Merkel et al, 1997, see [Appendix C](#)).

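### Triage SpO2, pulse and respiratory rate may serve as the pre-dose baseline with no time limit, so change before dosing enters the safety changes from baseline

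*Combined protocol and SAP*

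**What the plan says.** **Vital signs.** In section 4.2 Part 2 the baseline assessment includes measuring "vital signs (respiratory rate, pulse rate, oxygen saturation) if not already undertaken at" triage. In Table 1 the rows for SpO2, pulse rate and respiratory rate each carry an asterisk, explained below the table as "if data from assessments performed prior to ICF signature are part of normal ED procedure they can be used in the study". These three rows are ticked only under Visit 2 (baseline and treatment), not under screening. Section 4.3.4 calls for a baseline value but gives no window for it. Section 6.2.1 lists all three among the primary safety and tolerability variables. Section 7.4.1 summarises measured values and changes from baseline at each timepoint, with 95% confidence intervals, by age group and overall. Section 7.4 defines a change as the timepoint value minus the baseline value, without saying which reading is the baseline. The outline lists no control.

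**Pain.** Section 4.3.2 is explicit: "Immediately prior to administration of the IMP (baseline), the pain intensity will be rated using the applicable tool". Section 4.2 Part 2 says "The baseline assessment will include a repeat pain score, sedation score", and Table 1 footnote b lists a score at screening and a separate one "at baseline (before IMP administration), and at 10, 15, 20, 30, 45, 60 min post IMP". Section 4.2 Part 1 says triage data "can be utilized and transferred onto the screening electronic Case Report Form (eCRF", that is, to the screening form. The pain row in Table 1 nevertheless carries the same asterisk and is ticked under both visits.

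**The concern.** A change from baseline in a single-arm trial is read as what happened after the drug. That reading needs a baseline taken close to the dose. A triage reading comes before the consent discussion, the screening assessment and any settling of the child. If it is used as baseline, whatever changed in that interval is reported as change after CT001, and no comparator arm exists from which to subtract it.

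The variables concerned are the ones the plan uses to assess respiratory depression, oxygenation and cardiovascular stability for an opioid and ketamine combination in children. The outline also says that clinically relevant changes in values will be described, so judgements about individual children depend on the baseline as well as the group means.

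**Working it through.** The plan states no figure on this point, so there is none to reproduce. The check is a comparison of passages followed by short algebra.

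**1. Can a triage vital sign be the baseline?** The Table 1 asterisk admits readings taken before consent. The three vital-sign rows are ticked only under Visit 2, and a post-dose reading cannot precede consent, so the asterisk can apply only to the baseline value. Section 4.2 Part 2 says the same in words. Section 4.3.4 sets no window that would rule out an old reading. Section 4.2 asks for actual assessment times relative to dosing for pain scores, and the text has no matching request for vital signs. So the answer is yes, with no time limit.

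**2. What this does to the analysis.** For one child let T be the triage value, D the value just before dosing, and Y the value at a post-dose timepoint. Section 7.4 gives change = Y − baseline.

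- Baseline just before dosing: change = Y − D.
- Baseline from triage: change = Y − T = (Y − D) + (D − T).

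The error is D − T, the drift before any drug was given. If a share s of children have a triage baseline and their mean drift is m, then

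bias in mean change = s × m.

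This runs from 0 (every child re-measured, s = 0) to m (every child on a triage value, s = 1). For the same children it is identical at 10, 15, 20, 30, 45 and 60 minutes, so it would look like an immediate and sustained effect. It does not shrink as the sample grows, and the 95% confidence interval is centred on the shifted value. If s or m differs by age group, the by-age-group summaries are shifted by different amounts.

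**3. Direction.**

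- Settling before dosing (m below 0 for pulse and respiratory rate) adds an apparent fall. It can mimic a drug-related fall in respiratory rate and can hide a real rise in pulse.
- Rising distress before dosing (m above 0) does the reverse and can hide a real fall in respiratory rate.

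The documents give no value for s, m or the triage-to-dose interval, so the product cannot be evaluated.

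**4. Does the same hold for pain?** Four places require or imply a fresh score: section 4.3.2, the word repeat in section 4.2 Part 2, footnote b, and the routing of triage scores to the screening form. A fifth is indirect. Sedation is scored at baseline directly after pain (section 4.3.3 and footnote a), and the sedation row has no asterisk, so the paired pain score belongs in the study visit too. Against these stands only an asterisk attached to a whole row.

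**5. Which pain endpoints would a misread asterisk touch?** Those that use the baseline value: change from baseline, maximum change and the 30% reduction. As arithmetic only, a 2-point fall before dosing from a triage score of 6 is 2/6 = 33%, and from 5 (possible on NRS or FLACC) it is 2/5 = 40%. Either would meet the 30% criterion with no further change after dosing. From 7 it is 2/7 = 29%, which would not. The primary responder definition in section 6.1.1 is a score of 4 or below, so the size of the baseline score does not enter it.

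**The case against.** The strongest reply is that the consequence is contained. The analyses are descriptive. Section 7.4.1 also summarises the measured values at each timepoint, which owe nothing to the baseline. Section 6.3.2 counts clinically significant abnormal vital signs as adverse events whatever the change from baseline. Section 7 also announces a separate, more detailed analysis plan, which could define baseline. All of this is fair and limits the harm: a low saturation or respiratory rate would still be seen. It does not rescue the change-from-baseline summaries, which remain planned with confidence intervals. Nor can a later definition recover a pre-dose reading that was never taken.

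A reader might go further and infer that a triage pain score may also serve as the efficacy baseline, so that pre-treatment pain relief is credited to CT001. The documents do not support that. The asterisk cannot cover every tick in its row, because the pain row includes post-dose scores and the asterisked concomitant-medication row includes Day 2-7. It applies only where pre-consent data make sense, which for pain is screening. The triage clause in section 4.2 Part 2 most naturally attaches to the vital signs next to it; it cannot sensibly qualify a repeat score.

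Nor does it follow that the primary responder rate is inflated through the baseline value. The outline and section 7.4.1 do describe response relative to baseline, but for any child with a baseline of 5 or more, a score of 4 or below is a reduction whichever reading is called baseline. How a child already at 4 or below just before dosing is counted is a separate question, which this change would not settle.

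**Conclusion.** The point holds for vital signs. Section 4.2 Part 2 and Table 1 allow triage SpO2, pulse and respiratory rate as baseline without a time limit, and primary safety changes are calculated from them in an uncontrolled trial. The bias is the share of children with a triage baseline times their mean drift before dosing. It may go either way, and the documents cannot size it. It matters only if some sites use the allowance and if values move between triage and dosing. Both are plausible in an emergency department, but neither is quantified. It distorts a safety summary and is not evidence that benefit is overstated.

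For pain, the finding is a wording inconsistency: a row-level asterisk that sits badly with four clear statements. Only the secondary endpoints that use the baseline score would be exposed if a site misread it.

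**What to change.** - **Section 4.2 Part 2:** delete the clause that excuses baseline vital signs when triage has already recorded them.
- **Table 1:** remove the asterisk from the SpO2, pulse-rate and respiratory-rate rows. On the pain row, limit it to the screening assessment so that it agrees with section 4.3.2 and footnote b.
- **Section 7.4:** define baseline as the last timed value before the first IMP dose. Flag any child whose baseline comes from triage, so that changes can be shown with and without those children.

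The cost is protocol wording plus one brief oximeter and respiratory-rate reading per child just before dosing. For pain there is no added cost, because the pre-dose score is already required. No sample-size input is a baseline value, so the planned 113 and 150 are unaffected.
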